4 SURGERY , CHEMOTHERAPY AND IMAGING

Radiation therapy will be performed either preoperatively or postoperatively. This decision will be made by the attending surgeon and radiation oncologist. For patients in the preoperative cohort, surgery will be performed 4-12 weeks after completion of radiotherapy. This will consist of resection of all gross tumor with adequate margins, sampling of lymph nodes and any other areas suspicious for involvement by the sarcoma as clinically appropriate. For patients in the postoperative cohort, radiotherapy will begin 3-8 weeks following surgery.

Chemotherapy (standard of care as determined by medical oncology) may be given no sooner than day 30 after radiation therapy for the post-operative patients or day 30 after surgery if radiotherapy is pre-operative as deemed clinically appropriate by the attending surgeon and radiation oncologist.

CONFIDENTIAL

18F-EF5 PET Scan

Up to 4 weeks prior to treatment with either surgery or proton radiation, ^{18}F -EF5 will be administered in the Department of Nuclear Medicine in the Hospital of the University of Pennsylvania (HUP) or in the Department of Radiation Oncology in the Perelman Center for Advanced Medicine. Approximately 5mCi of ^{18}F -EF5 will be administered as an IV bolus (for details of ^{18}F -EF5 synthesis, see specific methods, below). After the injection of ^{18}F -EF5, subjects will be asked to remain in the Nuclear Medicine or Radiation Oncology waiting room during the free time before their PET/CT scan, where they may relax until they are required to go to the PET/CT scan room. There is no bathroom restriction during this time. The Scan will be performed at 180 minutes (evaluation of hypoxia) following injection. Subjects will be positioned on the PET-CT imaging bed comfortably with their head secured in the head hold of the PET instrument.

TIME (APPROXIMATELY)	SCHEDULE OF EVENTS
-30 minutes	Transport to nuclear medicine facility
-10 minutes	Placement of one intravenous line
0 minutes	Injection of ^{18}F -EF5 (\approx 5 mCi)
1-179 minutes	Free time
180 minutes	PET/CT Scan
215 minutes	Study completed

Table 3: ^{18}F -EF5 PET Protocol**Expected Adverse Events Associated with radioactive ^{18}F -EF5.**

The estimated radiation exposure from 5 mCi of ^{18}F -EF5 is 2.5 mGy (see section 2.4, p. 10). This is the equivalent of less than one year of exposure to natural background radiation (1 year exposure approximately 3.6 mGy assuming quality factor of 1). For comparison purposes, a bone scan is estimated to deliver an effective dose between 3.8 and 7.7 mGy (42). A body CT scan is estimated to deliver 6-16 mGy (42, 43). Therefore, the amount of radiation to which patients will be exposed by ^{18}F -EF5 PET scanning is well below that delivered by other standard radiological tests and is not expected to cause problems related to radiation exposure. ^{18}F -EF5 and EF5 are identical from a chemical standpoint. The amount of labeled drug will be less than 5 mg, compared with 1500 mg (for a 70 kg patient) of unlabeled drug. Therefore no chemical toxicity can be expected for the small additional amount of labeled drug.

Radiation Exposure Based on Pharmacokinetic Studies of ^{18}F -EF5 in Human Subjects

Potential radiation toxicities are limited by the short half-life of [^{18}F] of 1.83 hours. Clinical experience with other fluorine-18 labeled agents designed to image tumor hypoxia or other metabolic events confirms that the short half-life of [^{18}F] results in no significant radiation toxicity. In order to determine more precisely the radiation exposure from [^{18}F]-EF5, pharmacokinetic studies are currently underway. The "worst case scenario" would be if the entire dose of [^{18}F]-EF5 stayed within the body. If there were uneven biodistribution, certain organs might get a relatively higher dose such as is the case with the thyroid with radioactive iodine. For EF5, the major route of excretion is through the urinary bladder with substantial excretion via the gall bladder. Based on pharmacokinetic studies to date, bladder excretion is extremely consistent for each subject, with a typical rate of approximately 5% per hour. Therefore, the radiation risk from [^{18}F]-EF5 will be predicted to be nearly identical to that for the ^{18}F -FDG dose used in a routine clinical PET scan. The estimated dose to the subject based on data from [^{18}F]-EF5 administration in human subjects is about 0.025 mSv/MBq. This results in a radiation exposure of about 4 mSv for a standard subject getting 5 mCi, and is comparable to the annual background of about 3.6 mSv. As mentioned above, organs that concentrate the radiotracer get a higher dose. Therefore, the urinary bladder wall is expected to receive about 5 times this dose (20 mSv), and the gall bladder wall receives about 2.5 times (10 mSv).

Dose Rationale and Risk/Benefits

CONFIDENTIAL

This material is the property of the University of Pennsylvania. Do not disclose or use except as authorized in writing by the study sponsor

We have specified a dose range centered around 5 mCi (range: 2.5 – 7.5 mCi) since it is not possible to determine exactly how much [^{18}F] labeled drug will be made prior to its synthesis and purification. If an individual synthesis should produce less than 5 mCi, there is confidence that acceptable (although more noisy) data can be obtained with as little as 2.5 mCi. Yields lower than 2.5 mCi will not be used. Conversely, it would be difficult to accurately subdivide the final sterile dose if it was somewhat higher than 5 mCi. However, a dose greater than 7.5 mCi will be subdivided in order to administer a final subject dose of 5 mCi.

As described above, the estimated radiation exposure from 5 mCi of [^{18}F]-EF5 is 4 mSv based on the pre-clinical studies of [^{18}F]-EF5 dosimetry. This is the equivalent of about one year of exposure to natural background radiation. For comparison purposes, a bone scan is estimated to deliver an effective dose between 3.8 and 7.7 mSv (42). A body CT scan is estimated to deliver 6-16 mSv (42, 43). Therefore, the amount of radiation to which subjects will be exposed to by [^{18}F]-EF5 PET scanning is within the range of that delivered by other standard radiological tests and is not predicted to result in unacceptable radiation exposure. [^{18}F]-EF5 and EF5 are identical from a chemical standpoint. The amount of labeled drug will be less than 5 mg.

PHARMACEUTICAL INFORMATION - [^{18}F]-EF5

The chemical properties and synthesis of [^{18}F]-EF5 are described in detail in the INDs held by Varian Biosynergy Inc. and [name].

Availability of Study Drug

[^{18}F]-EF5 will be synthesized at the cyclotron facility of the University of Pennsylvania. [name] or his designate in the Department of Nuclear Medicine will maintain a complete log of each manufacture and disposition, including results of all SOPs.

Dispensing of Study Drug

Following the manufacture of [^{18}F]-EF5 at the PENN cyclotron facilities, it is hand-carried to the Department of Nuclear Medicine in the Hospital of the University of Pennsylvania or to the Department of Radiation Oncology in the Perelman Center for Advanced Medicine where the radioactivity is assessed. It is anticipated that the activity will be in the range of 2.5-7.5 mCi. For doses greater than 7.5 mCi, the study drug will be subdivided to ensure that the dose administered will be 5 mCi. [^{18}F]-EF5 will then be drawn into a sterile syringe for intravenous subject administration.

Treatment Regimen

[^{18}F]-EF5 will be administered by a qualified user in the Department of Nuclear Medicine in the Hospital of the University of Pennsylvania or in the Department of Radiation Oncology in the Perelman Center for Advanced Medicine. It will be administered as an IV bolus injection. The dose will be approximately 5 mCi (acceptable range: 2.5-7.5 mCi).

Destruction of Study Drug

If the entire study drug dose is administered, the radioactive syringe will be disposed of into the radioactive waste in the Department of Nuclear Medicine or in the Department of Radiation Oncology in the Perelman Center for Advanced Medicine. As the radioactive half-life of ^{18}F is 1.83 hours, we anticipate that by the end of a working day, the radioactive syringe can be safely disposed of in the standard biologic waste. In the event that the study drug is not administered or only partially administered, the radioactive syringe and its contents will be disposed of in the radioactive waste in the Department of Nuclear Medicine or in the Department of Radiation Oncology in the Perelman Center for Advanced Medicine. It will be subsequently disposed of in the standard biologic waste upon sufficient decay of its radioactivity.

CONFIDENTIAL

5 STUDY PROCEDURES

	Pre-treat	Day of F18-EF5 PET/CT Prior to injection	Weekly during RT	Visit prior to surgery	30 days post surg/RT ^{1*}	Q3 months for 2 years, then q6 months for years 3 - 5 after surgery/RT	Yearly (as long as the patient wishes to be followed)
Tests and Observations							
History and PE	X		X	X	X	X	X
ECOG PS	X						
Biopsy	X						
Urine Pregnancy Test		X ²					
Toxicity Assessment	X		X			X	
Tumor Measurement	X ¹			X		X	
18F-EF5 PET Scan (optional)	X ³						

1- *Post radiation/surgery follow-up schedule defined for each cohort in Section 6.

2- Urine pregnancy test is routinely performed prior to PET/CT scanning as departmental standard.

3 – Subjects may participate in study with or without performing 18F EF5 PET scan. This is a subject option.

Post-treatment Evaluation and follow-up

All subjects will be evaluated prior to initiation of treatment and weekly during the course of radiotherapy. For patients receiving pre-operative radiation, a visit will occur prior to surgery. This visit will involve an interval history and physical. All patients will be seen for a first post-operative/post-radiation office visit with either the attending radiation oncologist or surgeon no more than 30 days following surgery/radiotherapy or discharge from the hospital, whichever comes later. Pre-operative patients will be seen after surgery, weekly x 1 month, then every 2nd week x 1 month, then monthly for 3 months. Post-operative patients will be seen one month after surgery and then in 3 months. Follow up visits for pre-operative and post-operative patients will be with either the attending surgeon or radiation oncologist every 3 months for two years, and every 6 months thereafter for 3 years. These office follow-up visits will consist of an interval history and physical and imaging studies as clinically indicated. The wound complication endpoint will be scored at 4 months after surgery in the pre-operative group. Post-operative patients will be scored for fibrosis, edema and joint stiffness within 2 years after after radiation.

Assessment of Tumor Response

Tumor Response (RECIST criteria): RECIST criteria will only be evaluated after radiation just prior to surgery in the pre-operative patients. Post-operative patients will not be evaluated since they undergo complete resection of STS.

Target Lesions:

- **Complete Response (CR):** Disappearance of all target lesions.
- **Partial Response (PR):** At least a 30% decrease in the sum of the longest diameters of target lesion, taking as reference the baseline sum of the longest diameters.

CONFIDENTIAL

- **Progressive Disease (PD):** At least a 20% increase in the LD of the target lesions, taking as reference the smallest sum of the LD recorded since the treatment started or the appearance any new lesion(s)
- **Stable Disease (SD):** Neither sufficient shrinkage to qualify for PR nor sufficient increase to qualify for PD, taking as reference the smallest sum LD since the treatment started.

Non-Target Lesions:

- **Complete Response (CR):** Disappearance of all non-target lesions and normalization of tumor marker levels.
- **Incomplete Response/Stable Disease (SD):** Persistence of one or more non-target lesion(s) and/or maintenance of tumor marker levels above normal limits.
- **Progressive Disease (PD):** Unequivocal progression of existing non-target lesions or any new lesion(s)

Confirmation of Response (used only for studies with response as primary endpoint)

- To assign a PR or CR, changes in tumor measurement must be confirmed by repeat assessments no less than 4 weeks after the criteria for response are first met. (*Reflect this in your study procedures table in section 6*)
- To assign SD, measurements must have met the stable disease criteria at least once after study entry at "X" interval (*as defined by protocol*).

Failure

- **Local failure** is defined as: evidence of tumor growth in any direction beyond that present of the pre-treatment imaging studies or the appearance of tumor in tissues previously scored as sites of subclinical disease. The imaging studies are to be comparable in technical factors.
- **Marginal failure** is defined as appearance of tumor growth at the margin of the target volume
- **Nodal Failure:** Failure in regional lymph nodes.
- **Distant failure** is defined as appearance of tumor at sites beyond regional nodal and marginal site.
- **Progression-Free Survival:** duration measured from first day of treatment to first documented failure, death due to any cause or last patient contact alive.
- **Overall Survival:** Duration measured from first day of treatment until death due to any cause or last patient contact alive.
- Time to local failure, time to distant failure, PFS and OS will be calculated from **first day of radiation** in the pre-operative patients and calculated from **day of surgery** in the post-operative patients.

PET scan imaging and analysis

PET studies will be performed on a PET/CT scanner in the Department of Radiology in the Hospital of the University of Pennsylvania or in the Perelman Center for Advanced Medicine. PET scans will be processed with corrections for randoms, scatter, and attenuation before reconstruction. The randoms are subtracted directly (on-line) using a delayed coincidence window. The application of an accurate scatter correction method is necessary to achieve absolute quantification, and is particularly important for 3D PET. We have developed a Single-Scatter-Simulation (SSS) algorithm for this purpose (44) which has been extended for TOF data. The basic idea is to calculate from first principles the scatter distribution associated to an activity and scatter medium distribution, under the assumption that scatter is only due to single Compton scatter events. The assumption of single-event scatter is a good approximation for a system with good energy resolution, such as LYSO, particularly with a high energy threshold as used in the Gemini TF scanner. In practice, we use an estimate of the activity distribution from the reconstructed image of total counts, and the distribution of the

CONFIDENTIAL

scatter medium is obtained from the reconstructed transmission CT scan, which is also used for attenuation correction.

For TOF reconstruction, we use the list-mode reconstruction implemented by Philips that is based upon a TOF list-mode maximum-likelihood algorithm which was originally developed in our laboratory at the University of Pennsylvania (45). This algorithm models data corrections in the algorithm and uses consecutively ordered subsets to accelerate the reconstruction. The Poisson statistics of the data are preserved by using the data in their original form (i.e., without binning) and incorporate the physical effects of PET imaging in the system model. The TOF kernel is modeled as a one-dimensional Gaussian function along the LOR and is applied in both the forward-projection and back-projection operations. We reconstruct patient studies using the protocol defined at the University of Pennsylvania that uses unrelaxed OSEM ($\lambda=1$) with 33 subsets and stops after three iterations for practical reconstruction time. A fully 3D list-mode iterative reconstruction algorithm is computationally intensive and required specialize computer equipment and software development to implement in practice. Using a 10-node (dual CPU) computer cluster, the image processing with this algorithm proceeds in parallel with data acquisition and is typically completed for clinical whole-body (multi-bed) studies 10-30 minutes after the end of the acquisition, depending on the number of counts collected.

The data corrections and 3D reconstruction that have been described help to improve the accuracy of quantification of the studies, in particular tumor contrast. Nevertheless, we do not expect that full recovery of contrast of small tumors will be achieved. Typically this is possible only if the tumor size is large compared to the spatial resolution. For example, the contrast of a 2-cm tumor is only about 50% of its true value, assuming that the region-of-interest is equal to the size of the tumor. Our image reconstruction algorithm has the capability of incorporating the measured point spread function into the system model so that we can recover the spatial resolution loss that is more significant as the distance from the center of the field-of-view increases. The resolution recovery technique will be further developed and validated for the tumor studies that will be performed for this project.

Image registration of the PET images with other modalities (CT or MRI) will be performed using a mutual information algorithm developed at PENN and similar to the approach of Mattes (46). Our algorithm allows non-rigid, as well as rigid registration, using a set of user-defined correspondence points as constraints. For intra-patient comparisons between the PET scans and the MRI or CT, the fully automated rigid registration is expected to have sufficient accuracy.

Tumor ROIs will be drawn with the help of MRI and/or CT images. Tumor to normal tissue ratio will be determined in each voxel of the ROI.

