At the University of Pennsylvania, we see approximately 20 cases of extremity STS per year. We anticipate that with the availability of proton radiotherapy, these numbers may increase. We estimate an annual accrual of 12 subjects per year for each cohort. We will also treat patients either preoperatively or postoperatively from Walter Reed Army Medical Center. In addition, this protocol will be listed on our web site as a formal protocol and information of its availability will be made known to treating professionals throughout our satellites as well as other referring physicians. These patients, if treated preoperatively with radiation therapy, will be required to have their surgery at the Hospital of the University of Pennsylvania.

Early Withdrawal of Subjects

When and How to Withdraw Subjects?

Recurrent or Progressive Disease: Subjects who have clinical or radiologic evidence of recurrent disease will undergo an evaluation to document the nature of the abnormality. If recurrent or progressive cancer is diagnosed, the subject will be considered off study at that time.

Subject Participation: Subjects may be withdrawn if the subject decides to refuse continuation of treatment or follow-up. Subjects may also be withdrawn for non-compliance with the protocol or withdrawal of consent. The reasons for withdrawal will be documented.

PI Decision: Subjects may be withdrawn at any time during the study if the PI believes it is in the subject's best interest. In this event, the reasons for withdrawal will be documented.

Once the subject has discontinued treatment, the primary reason for discontinuing treatment must be clearly documented in the subject's records and on the CRF. The investigator will assess each subject for response at the time of withdrawal.

Every effort will be made to follow subjects off study for toxicity and survival. Survival will be followed for a minimum of 5 years by means of scheduled appointments and available medical records. Every effort will be made to follow for overall survival.

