Publishers, 1964). Patients will be assessed for fibrosis, joint stiffness and edema within 2 years of completion of radiotherapy.

Clinical Efficacy is defined for pre-operative patients as overall response rate (CR + PR according to RECIST criteria) which is scored after radiation and before surgery. Progression-Free Survival is defined from first day of treatment to first documented failure, death due to any cause or last patient contact alive. Overall Survival is defined from first day of treatment until death due to any cause or last patient contact alive. Time to local failure, time to distant failure, PFS and OS will be calculated from first day of radiation in the pre-operative patients and calculated from day of surgery in the post-operative patients.

Rules for Early Termination for Feasibility, Acute Toxicity and Wound Complication:

Bayesian probability calculations will be employed to define rules of early termination and end of trial evaluation for feasibility and safety. The tables below indicate termination rules after groups of 3 patients have been treated. Hundreds of patients with certain types of cancer have undergone radiation therapy with protons. Thus, we will assume some "prior" feasibility and safety data for protons delivered at the standard radiation dose for our Bayesian calculations. We will assume prior information equivalent to that of 6 treated patients, which is commonly required to establish feasibility and safety in a standard 3+3 phase I trial design.

Feasibility – conducted separately for each stratum

We will assume a beta (5,1) prior, which is information equivalent to feasibility established in 5 of 6 treated patients. A feasibility rate > 90% is considered acceptable. If the number of patients deemed feasible is less than or equal to the number in the table below then termination will be considered as it is highly unlikely that the feasibility rate is > 90%, as noted by the Bayesian posterior probabilities.

Bayesian Rule for Feasibility				
Patients treated	3	6	9	12
Patients who are feasible	1	4	6	9
Posterior Prob[feasibility rate >90%]	0.0	0.0	0.0	0.0
Action	Terminate enrollment			

Acute Toxicity – conducted separately for each stratum * excludes wound complication *

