6.2 PHASE II STUDY

Design and Objectives:

This stratified phase II trial is designed to evaluate early complications (e.g., wound complication in pre-operative patients) and late complications (e.g., fibrosis, joint stiffness and edema in post-operative patients). Patients with STS of the lower extremity only will be treated in the phase II study. Justification for enrolling lower extremity STS in phase II is that 80% of STS patients treated in the Department of Radiation Oncology have lower extremity STS and they are the subgroup who may benefit most from protons. For example in the study by O’Sullivan et al (Lancet 359, 2002), in pre-operative patients, the wound complication rate from photon radiotherapy in patients with lower extremity STS was 43% (30 events in 70 patients) compared to 5.5% (1 event in 18 patients) in upper extremity STS. 40 evaluable patients (including evaluable patients from the feasibility stage) will be enrolled in each stratum.

Endpoints:

Same endpoints as in Section 6.1: Wound complication, Fibrosis and joint stiffness, Edema, Acute toxicity, Late toxicity and Clinical Efficacy.

Evaluable for analysis:

For pre-operative patients, patients must have a minimum of 4 months of follow-up post-surgery to be evaluable and included in the phase II analysis. For post-operative patients, patients must have a minimum of 2 years of follow-up from the end of radiotherapy to be evaluable and included in the phase II analysis.

Rules for Early Termination for Wound Complications:

We will assume a beta (2,4) prior, which is information equivalent to wound complication in 2 of 6 treated patients. A wound complication rate >40% is considered unacceptable. If the number of patients with wound complications is greater than or equal to the number in the table below then termination will be considered as it is likely that the wound complication rate is >40%, as noted by the Bayesian posterior probabilities.

Bayesian Rule for Wound complication						
Patients treated & followed 4 months	1	2	2	3	3	4
Patients who experience wound complication	5	0	5	0	5	0
Posterior Prob[wound complication toxicity rate >40%]	8	1	1	1	1	1
		1	3	5	7	9
	0	0	0	0.	0.	0.
	.	.	.	8	7	7
	7	8	8	1	9	8
	6	5	2			
Action	Terminate enrollment					

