6.3 STATISTICAL ANALYSES

Pre-operative patients: Toxicity data will be graded and tabulated. A one-sample one-sided chi-square test will be performed to test the null hypothesis that the wound complication rate is 45% (same as photon). Patients must have a minimum of 4 months of follow-up after surgery to be evaluable for this analysis.

CONFIDENTIAL

This material is the property of the University of Pennsylvania. Do not disclose or use except as authorized in writing by the study sponsor

Post-operative patients: Toxicity data will be graded and tabulated. In the study by Davis et al (Radiother and Oncol 75, 2005), the grade 2+ fibrosis rate was 48%, joint stiffness 23% and edema 23%. Since fibrosis is the most common post-operative toxicity, it is considered the primary endpoint and a one-sample one-sided chi-square test will be performed at the 5% significance level to test the null hypothesis of 50% (same as photon). Joint stiffness and edema are less frequent toxicities and will be treated as secondary endpoints. The null hypothesis is that the grade 2 or higher rate is 25% (same as photon) for these endpoints. Patients must have a minimum of 2 years of follow-up after surgery to be evaluable for this analysis.

Acute toxicity (Late toxicity): Toxicities will graded and tabulated by stratum.

Clinical Efficacy: For pre-operative patients, the RECIST response rate (CR + PR based on RECIST) and 90% exact CI will be computed. For each stratum, time to local recurrence, time to distant recurrence, PFS and OS will be estimated by Kaplan-Meier analysis.

Exploratory Analyses of [¹⁸F]-EF5:

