With 12 patients per year enrolled to each stratum and accounting for required follow-up time for feasibility and toxicities, this study should be active for 7 years. Twelve pre-operative and 12 post-operative patients will be enrolled on the feasibility portion of the trial. If feasibility and safety are acceptable then 40 evaluable pre-operative patients and 40 evaluable post-operative patients with STS of the lower extremity (each group includes evaluable patients from the feasibility stage) will be enrolled in the phase II portion of the trial. Up to 50 pre-operative patients may need to be enrolled to yield 40 evaluable patients with lower extremity STS who undergo surgery and have 4 months of follow-up post-surgery. With 40 evaluable patients, there will be 84% power for a chi-square test at one-sided 5% type I error to test a grade 2 or higher wound complication rate of 45% versus an alternative rate of 25%.

Similarly, up to 50 post-operative patients may need to be enrolled to yield 40 evaluable patients with lower extremity STS who receive post-operative radiotherapy and remain on-study for 2 years from the end of radiotherapy. With 40 evaluable patients, there will be 83% power for a chi-square test at one-sided 5% type I error to test a grade 2 or higher fibrosis rate of 50% versus an alternative rate of 30%. In addition, there will be 80% power for chi-square tests at one-sided 2.5% type I error to test grade 2 or higher joint stiffness and

CONFIDENTIAL

edema, each with rates of 25% versus alternative rates of 9%. These secondary analyses will be tested at a 2.5% significance level, to control the overall type I error.

All correlative analyses of hypoxia and clinical outcome are exploratory. Results from this unique study will be used to estimate the magnitude of the associations for both RECIST response and time-to-event outcomes and will provide important guidance for future studies of the prognostic importance of hypoxia in STS patients.

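### The pre-operative RECIST response rate has no denominator of its own, and the general phase II evaluability rule, applied as written, would drop unresected progressors from it

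*Combined protocol and SAP*

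**What the plan says.** **Timing.** Section 5 (Assessment of Tumor Response) states that "RECIST criteria will only be evaluated after radiation just prior to surgery in the pre-operative patients". Section 6.1 defines clinical efficacy for this cohort as "overall response rate (CR + PR according to RECIST criteria) which is scored after radiation and before surgery". PFS, OS and times to local and distant failure are listed with it.

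**Analysis set.** Section 6.2 gives the phase II endpoints as "Same endpoints as in Section 6.1: Wound complication, Fibrosis and joint stiffness, Edema, Acute toxicity, Late toxicity and Clinical Efficacy". The next paragraph sets the evaluability rule: "For pre-operative patients, patients must have a minimum of 4 months of follow-up post-surgery to be evaluable and included in the phase II analysis". It makes no exception by endpoint.

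**Analysis.** Section 6.3 says "For pre-operative patients, the RECIST response rate (CR + PR based on RECIST) and 90% exact CI will be computed". It gives no denominator and no rule for a patient without surgery or without a pre-surgical measurement. Section 6.1 plans the same estimate for the feasibility stage, expects to carry it out in phase II, and adds no denominator either.

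**Withdrawal.** Section 2 (Early Withdrawal of Subjects) says "If recurrent or progressive cancer is diagnosed, the subject will be considered off study at that time". The same section requires the investigator to assess response when a subject is withdrawn.

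**Numbers.** Section 6.4: "Up to 50 pre-operative patients may need to be enrolled to yield 40 evaluable patients with lower extremity STS who undergo surgery" and complete 4 months of follow-up after it.

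**The concern.** Requiring follow-up after surgery makes sense for wound complications, which can only be observed after an operation. It has no bearing on tumour response, which is fixed beforehand. Section 4 places surgery 4 to 12 weeks after radiotherapy, which leaves time for progression to appear or for an operation to be cancelled. A patient who progresses and is not resected cannot accumulate post-surgical follow-up and so falls outside the phase II analysis as Section 6.2 defines it. Under the response categories in Section 5 that patient is progressive disease, hence a non-responder.

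At stake is a descriptive secondary estimate, the CR+PR rate with its 90% exact interval. It would describe patients who reached surgery and were followed, but would be read as describing patients given pre-operative protons. The exploratory comparison of response by EF5 signal would use the same selected set.

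**Working it through.** **Inputs.** From Section 6.4: 40 evaluable patients from up to 50 enrolled, and 84% power for 45% against 25% at one-sided 5%. From Section 6.3: a 90% exact interval for response. The documents give no expected response rate, so 10% to 50% in the evaluable set is an assumed range.

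**1. The plan's own figures.**
- Power, normal approximation: Φ((0.20 − 1.645·√(0.45·0.55/40)) / √(0.25·0.75/40)) = 0.849. Exact binomial: reject at 12 or fewer of 40, actual level 0.0386, power 0.821. Both lie within 2 points of the stated 84%.
- Enrolment: 40/(1 − 0.20) = 50, so the plan allows for up to 10 non-evaluable patients.
- Intervals: Clopper-Pearson 90% limits reproduce the two-sided entries of the 12-patient table in Section 6.1 to about 0.1 point (for example 3/12: 7.2 to 52.7).

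**2. Effect of the exclusion.** Let x be the responders among the 40 analysed, and let m be the treated patients excluded, all non-responders. The reported rate is x/40 and the all-treated rate is x/(40+m). The relative overstatement is (x/40)/(x/(40+m)) − 1 = m/40:
- m = 2: 5%
- m = 4: 10%
- m = 10: 25%

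Rates in %, with 90% exact intervals:

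| x | Reported, x/40 | m = 4, x/44 | m = 10, x/50 |
|---|---|---|---|
| 4 | 10.0 (3.5–21.4) | 9.1 (3.2–19.6) | 8.0 (2.8–17.4) |
| 8 | 20.0 (10.4–33.2) | 18.2 (9.4–30.4) | 16.0 (8.2–27.0) |
| 10 | 25.0 (14.2–38.7) | 22.7 (12.9–35.5) | 20.0 (11.3–31.6) |
| 16 | 40.0 (26.9–54.2) | 36.4 (24.3–49.9) | 32.0 (21.2–44.5) |
| 20 | 50.0 (36.1–63.9) | 45.5 (32.5–58.9) | 40.0 (28.3–52.6) |

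**3. Offset from excluded responders.** If k of the m excluded patients responded, the all-treated rate is (x+k)/(40+m). This equals x/40 when k = m·x/40. With m = 10, the bias cancels at k = 2 for x = 8 (10/50 = 20%) and at k = 2.5 for x = 10.

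**4. EF5 by response.** Let a and b be responders and non-responders among hypoxic tumours, and c and d the same among the others. If a fraction s of non-responders is kept regardless of hypoxia, the odds ratio is a·(s·d)/((s·b)·c) = ad/(bc), which is unchanged.

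**The case against.** The strongest reply is that the 4-month rule was never meant for response. Section 6.3 restates it explicitly for the wound-complication test, while the Clinical Efficacy paragraph refers simply to pre-operative patients. Read literally for every endpoint, Section 6.2 would also remove from overall survival any post-operative patient who died within 2 years of radiotherapy, which can hardly be intended. This stands as far as intent goes: the restriction on response is an inference from general wording. It does not supply a denominator, however. Section 6.2 remains the only analysis-set definition in the phase II plan, and even on the narrow reading nothing says how an unoperated or unmeasured patient is counted.

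A reader might infer that patients who never reach surgery have no response assessment. The documents do not support that. Section 2 calls for one at withdrawal, the definition in Section 6.1 can be read as a time window, and progression found at the pre-surgery visit can be scored as such. What remains is a conflict between that duty and the word only in Section 5.

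A reader might also take 25% as the expected inflation. It is a ceiling. The allowance of 10 also covers patients lost after surgery, who may have responded, and possibly upper-extremity feasibility patients (about 12 × 0.20 = 2.4, from the stated 80% lower-extremity share). A patient who progresses but is still resected and followed might stay in, unless the off-study rule removes them.

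Finally, response is secondary and untested, and no photon response benchmark is given, so there is no comparison for it to tilt. PFS in this cohort runs from the first day of radiation, so progression before surgery is an event there. All of this limits the importance of the point.

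**Conclusion.** The point holds for a descriptive secondary endpoint. The plan gives the response rate no denominator of its own, and the one general rule available would exclude unresected progressors from an outcome already determined. Loss of progressors can only raise the rate. The net direction also depends on any responders lost, so upward bias is possible but not certain.

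The size is m/40 in relative terms if all m excluded patients are non-responders, with an upper limit of 25% at m = 10. In absolute terms that ceiling is 2 points at a reported 10%, 5 points at 25% and 10 points at 50%. At 10/40 the 5-point shift lies well inside an interval 24.5 points wide (14.2 to 38.7). These figures rest on assumed response rates and on the planned maximum loss.

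The primary wound-complication test and its power are unaffected. A reader might infer that the EF5 association would be weakened. That is not established, because selection on response alone leaves the odds ratio unchanged. Attenuation would need the lost non-responders to be more hypoxic than those retained, and the documents give no information on that.

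**What to change.** - **Sections 6.2 and 6.3:** for the pre-operative cohort, limit the 4-month post-surgery rule to the wound-complication endpoint.
- **Section 6.3:** compute the response rate, its 90% exact interval and the EF5-by-response analysis on all pre-operative patients in the phase II population who started proton radiotherapy. Count progression as non-response, and count unassessed patients as non-responders in the main figure. Report the rate among assessed or operated patients as supportive.
- **Sections 2 and 5:** reconcile the single pre-surgical scoring with the response assessment at withdrawal. For a patient who does not reach surgery, state that the withdrawal assessment, or the imaging that led to the cancelled operation, is used.

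**Cost.** Wording only. No new procedure is needed, because the assessments named are already required or already done, and the sample size and primary test stay as they are. The reported rate may become slightly less favourable. Counting unassessed patients as non-responders is conservative and will understate response where the reason is unrelated to the tumour, such as refusal of surgery. The supportive rate lets the reader judge by how much.
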